9.2. Efficacy Analysis

All of the following VE analyses assume correct classification of suspected CDI cases for all case definitions.

Five (5) analysis populations (per-protocol-2, per-protocol-3, mITT-1, mITT-2, and mITT-3) will be defined for VE analyses.

- The per-protocol-2 population will include all randomized subjects who received at least 2 doses of the investigational product to which they were randomized and had no major protocol violations up to and including 14 days after Dose 2.
- The per-protocol-3 population will include all randomized subjects who received all 3 doses of the investigational product to which they were randomized and had no major protocol violations up to and including 14 days after Dose 3.
- The mITT-1 population will include all randomized subjects who received at least 1 dose of investigational product.
- The mITT-2 population will include all randomized subjects who received at least 2 doses of investigational product.
- The mITT-3 population will include all randomized subjects who received all 3 doses of investigational product.

The per-protocol-2 and per-protocol-3 populations will be the primary populations for efficacy analyses accounting for the time interval after dosing as given in [Table 6](#) and will be used for analyzing VE endpoints. The mITT-1, mITT-2, and mITT-3 populations will be supportive populations for efficacy analyses and will be used for analyzing VE endpoints from immediately or 14 days after receipt of each dose of investigational product.

9.2.1. Analysis of the Primary Endpoints

VE is defined as $VE = 100 \times (1 - IRR)$, where IRR is the infection rate ratio, the calculated ratio of first primary CDI incidence between the *C difficile* vaccine group and the placebo group. VE_i will be evaluated separately after 3 and after 2 doses. The 2 primary efficacy hypotheses are (in order of fixed-sequence testing):

1. $H_{03}: VE_3 \leq 20\%$ vs $H_{a3}: VE_3 > 20\%$, and
2. $H_{02}: VE_2 \leq 20\%$ vs $H_{a2}: VE_2 > 20\%$.

where H_{0i} and H_{ai} represent null hypothesis and alternative hypothesis, and VE_i ($i = 2, 3$) represents VE after at least 2 doses and after all 3 doses, respectively. For subjects with multiple primary CDI cases, only the first primary case will contribute to the VE calculation in each hypothesis test.

The primary efficacy hypotheses will be tested by a 1-sided test for $VE > 20\%$ by a fixed-sequence testing procedure, with testing order of H_{03} followed by H_{02} using the approach described in Chan and Bohidar,⁶³ accounting for follow-up time after vaccination. Statistical inference will be based on the lower alpha-adjusted confidence interval (CI) for VE_3 , and VE_2 .

If the study continues after all 3 of the interim analyses, once 66 first primary cases after 3 doses have accumulated for the final analysis, the hypothesis test H_{03} will be performed first, and the null hypothesis H_{03} will be rejected if there are 20 or fewer cases observed in the *C difficile* vaccine group (corresponding to a 2-sided lower bound of 96.4% exact CI $> 20\%$), assuming equal follow-up times. The lower bound of the 2-sided 96.4% exact CI corresponds to $\alpha = 0.018$ (one-sided) used for final testing in a GS design with a gamma(-2) efficacy boundary. Only if the hypothesis H_{03} is rejected, then hypothesis testing for H_{02} will be performed, at the same significance level for VE_2 for the final analysis. The statistical success criterion for H_{02} also corresponds to the lower bound of the 2-sided 96.4% CI for VE being $> 20\%$. If there is failure to reject the hypothesis H_{03} , the hypothesis test H_{02} will not be performed.

The statistical analysis specifications for the primary endpoints are summarized in Table 6.

Table 6. Statistical Analysis Specifications for the Primary Endpoints

Primary Endpoints	Time Period for Case Accrual	CDI Case Definition	Analysis Population	Hypothesis Testing ^a	Statistical Testing Method
CDI incidence of a first primary episode per 1000 person-years of follow-up	From 14 days after receipt of third dose of investigational product onwards	1	Per-protocol-3 (primary)	H_{03}	Exact binomial, incidence rate
CDI incidence of a first primary episode per 1000 person-years of follow-up	From 14 days after receipt of third dose of investigational product onwards	1	mITT-3 (supportive)	H_{03}	Exact binomial, incidence rate
CDI incidence of a first primary episode per 1000 person-years of follow-up	From immediately after receipt of third dose of investigational product onwards	1	mITT-3 (supportive)	H_{03}	Exact binomial, incidence rate
CDI incidence of a first primary episode per 1000 person-years of follow-up	From 14 days after receipt of second dose of investigational product onwards	1	Per-protocol-2 (primary)	H_{02}	Exact binomial, incidence rate

Table 6. Statistical Analysis Specifications for the Primary Endpoints

Primary Endpoints	Time Period for Case Accrual	CDI Case Definition	Analysis Population	Hypothesis Testing ^a	Statistical Testing Method
CDI incidence of a first primary episode per 1000 person-years of follow-up	From 14 days after receipt of second dose of investigational product onwards	1	mITT-2 (supportive)	H ₀₂	Exact binomial, incidence rate
CDI incidence of a first primary episode per 1000 person-years of follow-up	From immediately after receipt of second dose of investigational product onwards	1	mITT-2 (supportive)	H ₀₂	Exact binomial, incidence rate

Abbreviations: CDI = *Clostridium difficile* infection; mITT = modified intent-to-treat.

a. For the per-protocol populations, hypotheses H₀₂ and H₀₃ will be tested in the fixed order of H₀₃ followed by H₀₂.

9.2.1.1. Multiplicity Control for the Primary Endpoints

There are 2 primary efficacy hypotheses; H₀₃, followed by H₀₂, if H₀₃ is rejected. The study will be considered successful if H₀₃ is rejected.

There are 2 sources of multiplicity in the study. First, there are repeated analyses of the primary hypothesis H₀₃, at the interim and final analyses. Alpha adjustment due to the planned interim analyses is explained in [Section 9.5](#). The second source of multiplicity is the existence of multiple primary hypotheses. The overall type I error rate for all primary hypotheses is controlled by the fixed -sequence testing procedure as described in [Section 9.2.1](#). Testing hypothesis H₀₂ will be considered as final analysis at the type I error of 0.018 only if H₀₃ is rejected and a decision is made to proceed to the final analysis.

9.2.2. Analysis of the Secondary Endpoints

9.2.2.1. Analysis of the Secondary Efficacy Endpoints

The analyses of the secondary efficacy endpoints will be performed based on a variety of CDI case definitions, detailed in [Section 2.1](#), after the primary objectives are met. For the endpoints that combine data for subjects who fulfill case definition 1 and subjects who fulfill case definition 3, or case definitions 2 and 4, each subject will contribute only once to the analysis.

In the evaluation of the efficacy of 2 doses of *C difficile* vaccine, only cases starting after the receipt of the second dose but prior to the receipt of the third dose of investigational product will contribute to the VE calculation.

In order to control overall Type I error, and specifically the Type I error for the evaluation of the secondary objectives, an alpha level of 0.018 (one-sided) for the final analysis is split equally (the Bonferroni correction, alpha = 0.009, for each family evaluation) for the evaluation of the secondary objectives between the 3-dose family and the 2-dose family (at-least-2-dose/only-2-dose), after primary objectives are met.

Furthermore, within each family, the endpoints will be evaluated sequentially; that is, the subsequent endpoint is evaluated only if the criteria are met for the previous endpoints.

The analysis and the success criteria for the secondary objective evaluation are outlined below:

- For evaluating *C difficile* vaccine in reducing the incidence of CDI cases, the lower limit (LL) of 98.2% CI (2-sided) for $VE > 0$.
- For evaluating the efficacy of Pfizer's *C difficile* vaccine in reducing the severity of CDI in terms of the duration, the upper limit (UL) of 98.2% CI (2-sided) < 0 for the difference in mean duration of CDI between the vaccine group and the control group.
- For evaluating the efficacy of Pfizer's *C difficile* vaccine in reducing the severity of CDI in terms of the risk ratio, the UL of 98.2% CI (2-sided) < 1.0 for the ratio of the proportion of subjects experiencing CDI who have a non-protocol-related medically attended visit in the vaccine group to the proportion of the subjects in the control group.

CCI [REDACTED]

CCI [REDACTED]

[REDACTED]

[REDACTED]

[REDACTED]

9.4. Safety Analysis

The safety population will include all subjects who receive at least 1 dose of investigational product. The safety population for reactogenicity analysis after each dose will include subjects who received that dose and have e-diary information available. For safety analysis, subjects will be analyzed according to the investigational product received.

AEs will be categorized according to Medical Dictionary for Regulatory Activities (MedDRA) and will be summarized by vaccine group. All summaries of AEs will show the number and percentage of subjects experiencing at least 1 event and the number of events for each vaccine group. Two (2)-sided 95% CIs based on the Clopper-Pearson method will be presented for (S)AE percentages.

A 3-tier approach will be used to summarize AEs. Under this approach, AEs are classified into 1 of 3 tiers:

- Tier 1 events: These are prespecified events of clinical importance and are maintained in a list in the product's Safety Review Plan.
- Tier 2 events: These are events that are not tier 1 but are "common." A MedDRA preferred term is defined as a tier 2 event if there is an incidence of at least 1% in any vaccine group.
- Tier 3 events: These are events that are neither tier 1 nor tier 2 events.

The Miettinen and Nurminen method⁶⁴ will be used to derive the 95% CI for the risk difference between *C difficile* vaccine and placebo for the above tier 1 and tier 2 events. The p-value from Miettinen and Nurminen method will also be provided for tier 1 events.

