The B5091009 Phase 2 study, which assessed 2 antigen dose levels (100 and 200 µg) administered in combination with AIOH at Months 0, 1, and 6 or Days 1, 8, and 30 to healthy adults 65 to 85 years of age, demonstrated that both regimens and both dose levels administered were generally well tolerated. Local reactions were predominantly mild to moderate, with injection site pain being the most frequent manifestation. After Dose 2, local reactogenicity was greater when the vaccine was administered at Day 8 compared to Month 1, particularly for the 200-µg dose level. Systemic events were also predominantly mild to moderate and the incidences of individual events were similar between the placebo group, the 100-µg dose group, and the 200-µg dose group. Within each regimen, the overall AE incidence rates were also similar between the placebo, 100-µg, and 200-µg dose groups. For both regimens, serious adverse events (SAEs) were numerically higher in the 100-µg and 200-µg dose groups than in the placebo group. However, there was no pattern to these events and no safety concern was identified. Both studied dose levels resulted in substantial neutralizing antitoxin A and B titers, with the immunogenicity profile following 3 doses administered at Months 0, 1, and 6 being preferred. In addition, the 200-µg dose level was more immunogenic than the 100 µg dose level.

Pfizer considers the available information from Studies B5091001 and B5091009 with PF-06425090 to support a favorable benefit-risk profile for studies administering 3 doses of the *C difficile* vaccine at dose levels up to 200 µg formulated with AIOH, as a potential prevention against CDI.

Additional information for this compound may be found in the single reference safety document (SRSD), which for this study is the investigator's brochure (IB).

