2. STUDY OBJECTIVES AND ENDPOINTS

Primary Efficacy Objective(s):		Primary Efficacy Endpoint(s):

 To demonstrate that Pfizer's C difficile vaccine is effective in reducing the incidence of a first primary episode of CDI (see case definition 1).^a 		
 CDI incidence per 1000 person-years of follow-up, assessed during up to 2 time periods (each analysis will be performed only if the preceding one was successful): 
 After receipt of the third dose of investigational product onwards. After receipt of the second dose of investigational product onwards.
Primary Safety Objective(s):		Primary Safety Endpoint(s):

 To evaluate the safety profile of Pfizer's C difficile vaccine as measured by the percentage of subjects reporting local reactions and systemic events, AEs, and SAEs. 		
 Local reactions (pain, erythema, and induration), as self-reported on electronic diaries (e-diaries) for up to 7 days following each dose of investigational product. Systemic events (fever, vomiting, headache, fatigue, new or worsening muscle pain, and new or worsening joint pain), as self-reported on e-diaries for up to 7 days following each dose of investigational product. Nonserious AEs from the signing of the informed consent document (ICD) to 1 month after receipt of the third dose of investigational product. SAEs from the signing of the ICD to 6 months after receipt of third dose of investigational product.
Evaluation Order	Secondary Objective(s):	Secondary Endpoint(s):
	3-Dose Family	
1.	
 To evaluate the efficacy of Pfizer's C difficile vaccine in reducing: 
 The incidence of all CDI cases (see case definition 1 and case definition 2). 	
 CDI incidence per 1000 person-years of follow-up, assessed after receipt of the third dose of investigational product onwards.

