9.1. Sample Size Determination

This study is placebo-controlled, event-driven, and randomized with a 1:1 randomization ratio between subjects receiving *C difficile* vaccine and placebo.

With assumptions of a true adjusted VE of 66.5% after 3 doses of investigational product, 66 first primary CDI cases (meeting case definition 1 in the per-protocol-3 population [Section 2.1.1](#) and [Section 9.2.1](#)) will provide 89.8% power to conclude true VE of >20%, taking into consideration 3 interim analyses ([Section 9.5](#)) during the study.

The early efficacy stopping boundaries are based on a GS design⁶⁵ utilizing a single-binomial distribution, conditional on a total of 66 cases, assuming true VE of 66.5%, with 3 interim analyses at 30, 40 and 50 cases.⁶⁵ The same gamma[-2] alpha spending function that was used for the original statistical design is also used for this modified statistical design.

As this is an event-driven and GS study, the total enrollment number may vary depending on the assumptions of incidence rate of the primary endpoint, true VE, and potential early stop for efficacy or futility.

Update as Part of Amendment 2 (January 2019):

Based on the ongoing blinded review of pooled primary CDI events, the annual CDI incidence rate in the placebo group may be different from the assumed rate in the power calculation during the initial study design. Additional enrollment may be needed in order to maintain the study power of 90% (106 first primary CDI cases in the final analysis) to reject the null hypothesis of $VE \leq 20\%$. Assuming a true VE of 60% after 3 doses of investigational product and the true annual CDI rate in the placebo group of 0.552% to 0.516%, which is 8 to 14% lower than the previously assumed 0.6%, an additional 1369 to 2566 subjects may be needed to ensure the required number of first primary CDI cases.

In light of this, it is planned to enroll approximately 1700 additional subjects, giving a total of approximately 17,476 subjects. The pooled primary CDI event rate for the total population will continue to be monitored by the study team in a blinded manner and a further adjustment to enrollment may be required.

Update as Part of Amendment 4 (July 2020):

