5.2.1.2. Safety Data

All of the primary safety endpoints, including proportions of subjects reporting local reactions, systemic events, AEs, and SAEs, will be summarized with percentages and the exact 2-sided 95% CIs by vaccine group.

For tier 1 and tier 2 AEs, the difference in the percentages between *C difficile* vaccine and placebo will be provided. The Miettinen and Nurminen (1985)³ method will be used to derive the 95% CI for the risk difference between vaccine and placebo. The p-value from the Miettinen and Nurminen method will also be provided for tier 1 events.

The exact CI for a proportion will be computed using the F distribution. If r equals the number of responses and n equals the number of subjects, then it follows that $p = r/n$ is the estimate of the proportion of responses. An exact 95% CI (or Clopper-Pearson confidence limit) can be computed by solving the following 2 equations.

For the lower limit P_L and the upper limit P_U , use

$$p_L = \frac{rF_L}{(rF_L + (n - r + 1))} \quad \text{and} \quad p_U = \frac{(r + 1)F_U}{(n - r) + (r + 1)F_U}$$

where F_L is the quantile from the F distribution for $\alpha=0.025$, with numerator degrees of freedom equal to $2r$ and denominator degrees of freedom equal to $2(n-r+1)$. F_U is the quantile from the F distribution for $\alpha=0.975$, with numerator degrees of freedom equal to $2(r+1)$ and denominator degrees of freedom equal to $2(n-r)$. When r equals 0, F_L should be set equal to 1.0 so P_L equals 0. When r equals n , F_U should be set equal to 1.0 so P_U equals 1. The CI using the F distribution is described in Collett (1991).⁴

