6.1.2.2. Adverse Events and Serious Adverse Events

The number and percentage of subjects experiencing at least 1 AE/SAE and the number of events will be descriptively summarized by vaccine group for the overall safety population.

Tier 1 and tier 2 events, as defined in Section 3.7.1, will present the proportion of AEs observed in each vaccine group along with the point estimates and associated 95% CIs of the risk difference (the difference of incidence rates) between *C difficile* vaccine and placebo. For both tier 1 and tier 2, the 95% CIs will be calculated using the Miettinen and Nurminen method described in Section 5.2.1.2. The p-value from the Miettinen and Nurminen method will be presented for tier 1 events only.

AE and SAE displays will be sorted in descending order of point estimates of risk difference within system organ class.

Separate listings of AEs and SAEs will also be provided.

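### The proportions with any SAE and any AE are primary safety endpoints, yet the plan specifies no between-arm interval for either

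*Protocol*

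**What the plan says.** Protocol 2 lists among the primary safety endpoints "SAEs from the signing of the ICD to 6 months after receipt of third dose of investigational product", alongside nonserious AEs. The matching objective is framed as the percentage of subjects reporting them.

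The planned analysis has two layers.

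- **Overall proportions.** SAP 5.2.1.2 says that the primary safety endpoints, naming AEs and SAEs, "will be summarized with percentages and the exact 2-sided 95% CIs by vaccine group". SAP 6.1.2.2 says that subjects with at least one AE or SAE, and the number of events, "will be descriptively summarized by vaccine group for the overall safety population". Protocol 9.4 likewise gives Clopper-Pearson 95% CIs for AE and SAE percentages by group.
- **Individual events.** Protocol 9.4 and SAP 5.2.1.2 and 6.1.2.2 give a risk difference with a Miettinen-Nurminen 95% CI to tier 1 and tier 2 events, and a p-value to tier 1 events. Tier 1 is a list in the Safety Review Plan; SAP 3.7.1 allows that it may have no entries. Tier 2 is defined by frequency: "A MedDRA preferred term is defined as a tier 2 event if there is an incidence of at least 1% in any vaccine group".

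On the earlier data, Protocol 1.2.3.3 states: "For both regimens, serious adverse events (SAEs) were numerically higher in the 100-µg and 200-µg dose groups than in the placebo group". The next sentence reads: "However, there was no pattern to these events and no safety concern was identified".

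**The concern.** The plan already contains a suitable method for comparing the arms, but the tier definitions do not bring that method to the aggregate. Tier 2 membership is a property of a preferred term, and any SAE is not one. The primary safety endpoint for SAEs is therefore reported as two separate percentages, each with its own interval, and nothing in the plan puts an interval on their difference.

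This matters a little more than usual here because the overall SAE count is where the protocol reports a numerical imbalance in Phase 2. A trial of this size can say how large an SAE excess its data exclude. Without a planned interval on the difference, that statement is left to the reader, or to a choice made after the results are known.

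**Working it through.** **Inputs**

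- Total enrollment: Protocol 9.1, "giving a total of approximately 17,476 subjects". Allocation is 1:1 (Protocol 3).
- Tier 2 threshold: 1% in either group (Protocol 9.4).
- SAE rate: not given in either document. I assume 5%, 10% and 15% to show a range.
- Safety population: at least one dose (Protocol 9.4). I take it as equal to enrollment, which is slightly optimistic.

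**1. Check of the enrollment figure.** The worked example in SAP 5.2.2.1 treats 7,100 placebo subjects as 90% of the initially planned placebo arm: 7,100 / 0.90 = 7,889 per arm, or 15,778 in total. Adding the roughly 1,700 subjects of Amendment 2 gives 17,478, which agrees with 17,476. Per arm: 17,476 / 2 = 8,738.

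**2. What the tier 2 threshold means.** 0.01 × 8,738 = 87.38, so a preferred term needs 88 subjects in at least one arm. It does not need 88 in each.

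**3. Precision of the missing interval when the observed rates are equal.** The Miettinen-Nurminen interval is the set of differences d for which

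|p1 − p0 − d| / √{[r1(1 − r1)/n1 + r0(1 − r0)/n0] × N/(N − 1)} ≤ 1.96,

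where r1 and r0 are the maximum-likelihood rates under r1 − r0 = d, and N = n1 + n0. At this sample size the simple approximation 1.96 × √[2p(1 − p)/n] gives the same answer to two decimals:

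| Assumed SAE rate, both arms | Approximation | Miettinen-Nurminen half-width (points) |
|---|---|---|
| 5% | 1.96 × √(0.0950/8,738) = 0.0065 | 0.65 |
| 10% | 1.96 × √(0.1800/8,738) = 0.0089 | 0.89 |
| 15% | 1.96 × √(0.2550/8,738) = 0.0106 | 1.06 |

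At 10% in both arms, for example, the interval would be −0.89 to 0.89 points, so an excess above 0.89 points would be excluded.

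**4. An example with a difference.** Take 961 vaccine and 874 placebo subjects with any SAE, that is 11% against 10%. The difference is 961/8,738 − 874/8,738 = 1.00 point, with a Miettinen-Nurminen 95% CI of 0.09 to 1.91.

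**5. What the planned table would show for the same data.** The exact 95% CIs would be 10.35% to 11.67% for vaccine and 9.38% to 10.65% for placebo. Neither gives the range of differences compatible with the data.

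**The case against.** The strongest reply is that this is a gap in presentation and nothing is hidden. Counts, percentages and exact intervals are planned for each arm. SAP 6.1.2.2 sorts AE and SAE displays by the point estimate of the risk difference, so imbalances in individual terms are brought to the top, and separate listings are provided. The external data monitoring committee can review unblinded safety data throughout (Protocol 9.6, SAP 7.1). Anyone with the counts can compute the interval. All of this stands, and it is why the point is minor. It does not supply a prespecified interval for the aggregate.

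Several stronger readings are tempting, and the documents do not support them.

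- A reader might infer that terms at 1% or more are the only ones with a between-arm interval. Tier 1 events get the same interval at any incidence, plus a p-value.
- A reader might infer that most SAE terms will get no interval. That is plausible, but the documents give no SAE rates by term and do not show the tier 1 list. The words in SAP 3.7.1 allow an empty list; they do not show that it is empty.
- A reader might take the Phase 2 imbalance as an unresolved safety signal. The protocol gives no counts, and its next sentence reports no pattern and no safety concern.
- A reader might say that a percentage threshold makes a larger trial look less closely. A 1% incidence is the same incidence at any size, and the per-arm intervals narrow as the trial grows. Only the raw count needed for tier 2 rises.
- A reader might charge the plan with comparing arms by whether their intervals overlap. No section proposes that. The example in step 5 shows only that two per-arm intervals do not replace an interval for the difference.

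**Conclusion.** The point holds, as a minor and inexpensive improvement. Any SAE and any AE are primary safety endpoints with per-arm exact intervals only. The risk-difference interval goes to tier 1 events and to preferred terms at 1% or more in either arm, and neither document extends it to an aggregate. The tier 1 list could in principle do so, but it is not available here and nothing suggests that it does.

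The size of the loss depends on an SAE rate that the documents do not give. Over an assumed 5% to 15% in both arms, with about 8,738 treated per arm, the missing interval would have a half-width of about 0.65 to 1.06 points. That is narrow enough to be informative whether it reassures or not.

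The documents do not support a broader criticism of the tier system. How to handle rare individual terms is a trade-off between detail and the number of unadjusted intervals, and the plan's choice is defensible.

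**What to change.** In Protocol 9.4 and SAP 5.2.1.2 and 6.1.2.2, add the risk difference between vaccine and placebo with its Miettinen-Nurminen 95% CI for the proportion of subjects with any SAE and with any AE. Any related SAE and death can be added at the same cost, because causality and deaths are already recorded (Protocol 8.1.5 and 6.1). Give no p-values for these rows, and add a footnote that the intervals are not adjusted for multiplicity. Leave the tier rules for individual preferred terms unchanged.

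The cost is a few sentences in the SAP and a few table columns, using collected data and a method already in the plan. The downside is a small number of further unadjusted intervals, one of which could exclude zero by chance; the footnote covers this.
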